6.0 Study Population

6.1 Inclusion and exclusion criteria (questionnaire outcomes)

Inclusion criteria

Diagnosis for asthma (confirmed by diagnostic Read code)

Age ≤65 years at index date for main outcomes, all ages for exploratory

Two years of continuous practice data comprising 2-year data prior to questionnaire

Asthma questionnaire returned

Prescription of Aerochamber[®] or Volumatic[®] spacer prior to the questionnaire

≥2 separate prescriptions of non extrafine beclomethasone in the baseline year prior to the index date

Exclusion criteria

Received multiple types of ICS or FDC ICS/LABA during the baseline period or at the index date

Prescribed both Aerochamber and Volumatic spacers

Table 6: Inclusion and exclusion criteria for questionnaire outcomes

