7.1 Demographic and baseline variables for patient questionnaire outcomes

- Gender (male/female)

- Age of patient (years, at index date)
- Body Mass Index (BMI, at time nearest index date, calculated from height and weight data if available, otherwise taken from practice-recorded BMI value, detailed definition in Appendix 1)
- Smoking status (identified by Read code, closest to index date)
- SABA daily dose calculated 1 year prior to index date*
- Percentage predicted peak flow (closest to index date)
- Total cumulative ICS dose
- Spacer type
- Total cumulative non-extrafine beclomethasone dipropionate therapy
- Duration of ICS therapy
- Number of exacerbations (ATS/ERS 2015 consensus definition[†]) from 1 year prior to index date
- Number of oral corticosteroid prescriptions from 1 year prior to index date
- Number of antibiotic prescriptions for lower respiratory tract infections from 1 year prior to index date
- History of comorbidities related to asthma:
 - Pneumonia (Read code diagnosis from 1 year prior to the index date)
 - Diabetes (Read code diagnosis and/or antidiabetic drugs ever prior to the index date)
 - Ischaemic heart disease (Read code diagnosis before one year prior to the index date)
 - Rhinitis (Read code diagnosis, including chronic and allergic rhinitis and prescriptions for nasal steroids between one year prior to index date)
 - Eczema (Read code diagnosis between one year prior to index date)
 - Osteoporosis (Read code diagnosis between one year prior to the index date)
 - Charlson Comorbidity Index (based on Read code diagnoses between one year prior to index date, detailed definition in Appendix 1)

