7.2 Demographics and baseline variables for database outcomes

- Gender (male/female)

* Calculated as average number of puffs per day over the year multiplied by strength (in µg);
i.e. $\frac{\text{Number of inhalers} \times \text{doses per inhaler}}{365} * \text{strength}$

† See appendix 1 for definitions

- Age of patient (years, at index date)
- Body Mass Index (BMI, at time nearest index date, calculated from height and weight data if available, otherwise taken from practice-recorded BMI value, detailed definition in Appendix 1)
- Smoking status (identified by Read code, closest to index date)
- SABA daily dose calculated in baseline prior to index date*
- Percentage predicted peak flow (peak flow predicted, closest to index date)
- Total cumulative ICS dose
- Total cumulative non-extrafine beclomethasone dipropionate therapy
- Duration of ICS therapy
- Number of exacerbations (ATS/ERS 2015 consensus definition[†]) prior to index date
- Number of oral corticosteroid prescriptions prior to index date
- Number of antibiotic prescriptions for lower respiratory tract infections prior to index date
- History of comorbidities related to asthma:
 - Pneumonia (Read code diagnosis in the year prior to the index date)
 - Diabetes (Read code diagnosis and/or antidiabetic drugs ever prior to the index date)
 - Ischaemic heart disease (Read code diagnosis prior to the index date)
 - Rhinitis (Read code diagnosis, including chronic and allergic rhinitis and prescriptions for nasal steroids prior to index date)
 - Eczema (Read code diagnosis prior to index date)
 - Osteoporosis (Read code diagnosis prior to the index date)
 - Charlson Comorbidity Index (based on Read code diagnoses in the year prior to index date, detailed definition in Appendix 1)

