- There is greater variation in weights between conditions and the Charlson Index (the sum of the weights) can be treated as a continuous variable (limited to the range 0-50) for the purposes of risk adjustment.

The weights, codes and conditions used in this study are summarised in the table below.

Table 9: Co-morbid conditions and scores used in the Charlson Co-morbidity Index (CCI)

Condition	Condition name	ICD-10 codes	Weight
1	Acute myocardial infarction	I21, I22, I23, I252, I258	5
2	Cerebral vascular accident	G450, G451, G452, G454, G458, G459, G46, I60-I69	11
3	Congestive heart failure	I50	13
4	Connective tissue disorder	M05, M060, M063, M069, M32, M332, M34, M353	4
5	Dementia	F00, F01, F02, F03, F051	14
6	Diabetes	E101, E105, E106, E108, E109, E111, E115, E116, E118, E119, E131, E131, E136, E138, E139, E141, E145, E146, E148, E149	3
7	Liver disease	K702, K703, K717, K73, K74	8
8	Peptic ulcer	K25, K26, K27, K28	9
9	Peripheral vascular disease	I71, I739, I790, R02, Z958, Z959	6
10	Pulmonary disease	J40-J47, J60-J67	4
11	Cancer	C00-C76, C80-C97	8
12	Diabetes complications	E102, E103, E104, E107, E112, E113, E114, E117, E132, E133, E134, E137, E142, E143, E144, E147	-1
13	Paraplegia	G041, G81, G820, G821, G822	1
14	Renal disease	I12, I13, N01, N03, N052-N056, N072-N074, N18, N19, N25	10
15	Metastatic cancer	C77, C78, C79	14
16	Severe liver disease	K721, K729, K766, K767	18
17	HIV	B20, B21, B22, B23, B24	2

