Oral corticosteroid prescriptions	N (% non-missing)	x (x)	x (x)	x (x)
	Mean (SD)	x (x)	x (x)	x (x)
	Median (IQR)	x (x, x)	x (x, x)	x (x, x)
Antibiotic prescriptions for LRTI	N (% non-missing)	x (x)	x (x)	x (x)
	Mean (SD)	x (x)	x (x)	x (x)
	Median (IQR)	x (x, x)	x (x, x)	x (x, x)
% Predicted Peak Flow	N (% non-missing)	x (x)	x (x)	x (x)
	Mean (SD)	x (x)	x (x)	x (x)
	Median (IQR)	x (x, x)	x (x, x)	x (x, x)

Table 29: Summary statistics for diagnoses of co-morbidities at baseline

		Volumatic®	Aerochamber®	p-value
Total (%)		x (x)	x (x)	x (x)
Pneumonia	N (% non-missing)	x (x)	x (x)	x (x)
	Mean (SD)	x (x)	x (x)	x (x)
	Median (IQR)	x (x, x)	x (x, x)	x (x, x)
Diabetes	N (% non-missing)	x (x)	x (x)	x (x)
	Mean (SD)	x (x)	x (x)	x (x)
	Median (IQR)	x (x, x)	x (x, x)	x (x, x)
Ischaemic heart disease	N (% non-missing)	x (x)	x (x)	x (x)
	Mean (SD)	x (x)	x (x)	x (x)
	Median (IQR)	x (x, x)	x (x, x)	x (x, x)
Rhinitis	N (% non-missing)	x (x)	x (x)	x (x)
	Mean (SD)	x (x)	x (x)	x (x)
	Median (IQR)	x (x, x)	x (x, x)	x (x, x)
Eczema	N (% non-missing)	x (x)	x (x)	x (x)
	Mean (SD)	x (x)	x (x)	x (x)
	Median (IQR)	x (x, x)	x (x, x)	x (x, x)
Osteoporosis	N (% non-missing)	x (x)	x (x)	x (x)
	Mean (SD)	x (x)	x (x)	x (x)
	Median (IQR)	x (x, x)	x (x, x)	x (x, x)
Charlson comorbidity index, n (%)	0	x (x)	x (x)	x (x)
	1-4	x (x)	x (x)	x (x)
	5+	x (x)	x (x)	x (x)

		Volumatic®	Aerochamber®	p-value
Total (%)		x (x)	x (x)	x (x)
Age (years)	N (% non-missing)	x (x)	x (x)	x (x)
	Mean (SD)	x (x)	x (x)	x (x)
	Median (IQR)	x (x, x)	x (x, x)	x (x, x)
Gender, n (%)	Male	x (x)	x (x)	x (x)
	Female	x (x)	x (x)	x (x)
BMI (kg/m ²)	N (% non-missing)	x (x)	x (x)	x (x)
	Mean (SD)	x (x)	x (x)	x (x)
	Median (IQR)	x (x, x)	x (x, x)	x (x, x)
BMI (categorised), n (%)	Underweight	x (x)	x (x)	x (x)
	Normal	x (x)	x (x)	x (x)
	Overweight	x (x)	x (x)	x (x)
	Obese	x (x)	x (x)	x (x)
Smoking status, n (%)	Current smoker	x (x)	x (x)	x (x)
	Ex-smoker	x (x)	x (x)	x (x)
	Mean (SD)	x (x)	x (x)	x (x)
	Median (IQR)	x (x, x)	x (x, x)	x (x, x)
Average SABA daily dose	N (% non-missing)	x (x)	x (x)	x (x)
	Mean (SD)	x (x)	x (x)	x (x)
	Median (IQR)	x (x, x)	x (x, x)	x (x, x)
Average SABA daily dose (categorised), n (%)	Low	x (x)	x (x)	x (x)
	Medium	x (x)	x (x)	x (x)
	High	x (x)	x (x)	x (x)
	Medium	x (x)	x (x)	x (x)
	High	x (x)	x (x)	x (x)
	Median (IQR)	x (x, x)	x (x, x)	x (x, x)
FEV ₁ /FVC ratio	N (% non-missing)	x (x)	x (x)	x (x)
	Mean (SD)	x (x)	x (x)	x (x)
	Median (IQR)	x (x, x)	x (x, x)	x (x, x)

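### The Charlson index gives 4 points for a code range that includes asthma, the entry diagnosis, so band 0 is empty or reflects asthma coding, and mild comorbidity moves into 5+

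*Protocol*

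**What the plan says.** - **Codes and weights.** Protocol section 15.1.3 introduces its table (captioned Table 9) with "The weights, codes and conditions used in this study are summarised in the table below". Condition 10, "Pulmonary disease", is defined as "J40-J47, J60-J67" and carries weight 4. The total is limited to 0 to 50.
- **Entry criterion.** Section 6.1 requires "Diagnosis for asthma (confirmed by diagnostic Read code"), and section 6.2 has the same criterion. Neither sets a time window for the diagnosis.
- **Source and window of the index.** For the questionnaire cohort, section 7.1 has the index "based on Read code diagnoses between one year prior to index date". For the database cohort, section 7.2 has it "based on Read code diagnoses in the year prior to index date".
- **Reporting.** The mock comorbidity tables in Appendix 2 show the index as 0, 1-4 and 5+, overall and in each age and dose subgroup.
- **A possible limit.** Section 15.1.3 also says that the revised hospital version counts secondary diagnosis fields only (DIAG02 to DIAG14).

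**The concern.** A comorbidity index should describe illness other than the disease under study. In ICD-10, J45 and J46 are the asthma codes. The protocol does not spell this out, but it follows from the classification that the table uses. Both lie inside the first range of condition 10, and no section takes them out, so the study disease is scored as a 4-point comorbidity.

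The bottom band would then not identify patients free of comorbidity. Patients with one lightly weighted condition would sit in the same band as patients with heart failure or cancer. The comorbidity tables, which should show whether the two spacer groups are alike, would be mislabelled. The same would pass into matching or adjustment if the index were chosen for either.

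**Working it through.** The only figure the plan states here is the weight of 4, a table entry with no formula behind it. The check adds it to the table's other weights and reads off the bands.

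**Inputs (section 15.1.3).** Pulmonary disease 4. The other 16 conditions are:
- five with weights below 5: connective tissue disorder 4, diabetes 3, HIV 2, paraplegia 1, diabetes complications -1;
- eleven with weights of 5 to 18: myocardial infarction 5, peripheral vascular disease 6, liver disease 8, cancer 8, peptic ulcer 9, renal disease 10, cerebral vascular accident 11, congestive heart failure 13, dementia 14, metastatic cancer 14, severe liver disease 18.

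**Formula.** Let S be the sum of the weights of the other 16 conditions. The score is S if asthma is not scored and S + 4 if it is, limited to 0 to 50. The bands come from Appendix 2.

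| Other condition | S | Band | S + 4 | Band |
|---|---|---|---|---|
| None | 0 | 0 | 4 | 1-4 |
| Diabetes complications only | -1, cut to 0 | 0 | 3 | 1-4 |
| Paraplegia | 1 | 1-4 | 5 | 5+ |
| HIV | 2 | 1-4 | 6 | 5+ |
| Diabetes | 3 | 1-4 | 7 | 5+ |
| Connective tissue disorder | 4 | 1-4 | 8 | 5+ |
| Any one of the eleven | 5 to 18 | 5+ | 9 to 22 | 5+ |

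The pattern is general. S cannot be below -1, because only one weight is negative. So S of -1 or 0 becomes 3 or 4 (band 1-4), S of 1 to 4 becomes 5 to 8 (band 5+), and S of 5 or more stays in 5+.

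**All combinations.** The 16 other conditions give 2^16 = 65,536 combinations:
- asthma not scored: 3 in band 0, 14 in 1-4 and 65,519 in 5+;
- asthma scored: 0 in band 0, 3 in 1-4 and 65,533 in 5+. The three are asthma alone, asthma with diabetes complications, and asthma with diabetes complications and paraplegia.

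These are counts of possible patterns, not of patients.

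**Two cases.**
1. *Asthma is coded in the baseline year for everyone.* Band 0 is empty, 1-4 is essentially asthma alone, and 5+ is almost any other scored condition.
2. *Asthma is coded that year for some only.* This is possible because the entry diagnosis has no time window and the index has one year. A patient with no other condition is then in 0 or 1-4 according to asthma coding alone. A patient with only diabetes, connective tissue disorder, HIV or paraplegia is in 1-4 or 5+ for the same reason.

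**The case against.** - **The secondary-diagnosis rule.** In the hospital scheme the primary diagnosis is not scored, so one could argue that asthma, as the index disease, drops out. But the rule concerns numbered hospital diagnosis fields. Sections 7.1 and 7.2 build the index from Read codes, and the protocol gives no Read-code equivalent, so the safeguard is not carried over.
- **The Read code list is not shown.** The table is in ICD-10, and a translation could leave asthma out. That is fair. But the protocol says that these codes are the ones used in the study, and a faithful translation would include asthma.
- **The bands still measure something.** This stands. A reader might infer that all three bands are meaningless. They are not: 5+ cannot be reached on pulmonary disease alone, and the eleven conditions weighted 5 or more fall there in any case.
- **The harm to matching is not established.** This also stands. A reader might infer that pairs will be spent on coding behaviour. Section 8.3 names disease co-morbidity only as a candidate. It names neither the index nor these bands, and section 15.1.3 allows the index to be treated as continuous. If every patient scored the 4 points, a continuous score would shift by a constant (apart from the limits at 0 and 50) and cost no pairs.
- **No difference between spacers is shown.** Both groups must have asthma, and nothing in the protocol suggests that asthma coding differs by spacer. Diabetes, one of the four conditions that change band, is also listed as a separate baseline variable.

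**Conclusion.** The point holds as a minor but definite error in a baseline definition. Followed as written, the index scores the study disease. Each patient with scored asthma who would otherwise be in band 0 appears in 1-4, and each who would otherwise be in 1-4 appears in 5+. The 0 versus 1-4 split therefore does not separate patients by comorbidity, while 5+ does so at a lower threshold than intended.

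This rests on two assumptions: that J45 and J46 are carried into the Read code list for condition 10, and that the secondary-diagnosis rule has no unstated equivalent in primary care data. The number of patients reclassified cannot be worked out, because the protocol gives neither comorbidity frequencies nor the share with asthma coded in the baseline year.

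The effect is on the comorbidity tables, and on matching or adjustment only if the index is used there. The primary outcome, the 13% margin and the group sizes of 293 and 147 do not depend on it.

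**What to change.** In Appendix 1, section 15.1.3, state that for this study the asthma codes (J45 and J46, with their Read equivalents) are not counted under condition 10. Keep the other codes of that condition: dropping the whole row would discard genuine pulmonary comorbidity. Say also that the secondary-diagnosis rule describes the hospital version and is not applied to Read codes, so that a reader does not take it as the safeguard.

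Apply the 0, 1-4 and 5+ bands to the corrected score. Band 0 then means no net positive comorbidity score. Diabetes complications alone (-1, cut to 0), or with paraplegia (-1 + 1 = 0), still fall there.

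The cost is a sentence or two in the appendix and one edit to the code list. No new data are needed, and the sample size does not change.

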15.2 Appendix 2: Mock baseline results tables

15.2.1 Primary analysis

	Aerochamber®	Volumatic®	95% Confidence Interval	p-value
Total number of patient reported adverse events, n (%)	x (x)	x (x)	x (x)	X
Continual sore mouth	x	x-x	x	X
Oral thrush	x	x-x	x	X
Bruising	x	x-x	x	X
Hoarse Voice	x	x-x	x	X
Abnormal weight gain	x	x (x)	x (x)	X
Cough	x	x (x)	x (x)	X

Table 10: Total patient questionnaire reported adverse events

	Aerochamber®	Volumatic®	95% Confidence Interval	p-value
Total number of patient reported adverse events, n (%)	x (x)	x (x)	x (x)	X
Continual sore mouth	x	x-x	x	X
Oral thrush	x	x-x	x	X
Bruising	x	x-x	x	X
Hoarse Voice	x	x-x	x	X
Abnormal weight gain	x	x (x)	x (x)	X
Cough	x	x (x)	x (x)	X

Table 11: Patient questionnaire reported outcomes for patients <16

	Aerochamber®	Volumatic®	95% Confidence Interval	p-value
Total number of patient reported adverse events, n (%)	x (x)	x (x)	x (x)	X
Continual sore mouth	x	x-x	x	X
Oral thrush	x	x-x	x	X
Bruising	x	x-x	x	X
Hoarse Voice	x	x-x	x	X
Abnormal weight gain	x	x (x)	x (x)	X
Cough	x	x (x)	x (x)	X

Table 12: Patient questionnaire reported outcomes for patients aged 16-65

	Aerochamber®	Volumatic®	95% Confidence Interval	p-value
Total number of patient reported adverse events, n (%)	x (x)	x (x)	x (x)	X
Continual sore mouth	x	x-x	x	X
Oral thrush	x	x-x	x	X
Bruising	x	x-x	x	X
Hoarse Voice	x	x-x	x	X
Abnormal weight gain	x	x (x)	x (x)	X
Cough	x	x (x)	x (x)	X

Table 13: Patient questionnaire reported outcomes for patients prescribed <1000 µg non extra fine beclomethasone

	Aerochamber®	Volumatic®	95% Confidence Interval	p-value
--	--------------	------------	-------------------------	---------

Total number of patient reported adverse events, n (%)	x (x)	x (x)	x (x)	X
Continual sore mouth	x	x-x	x	X
Oral thrush	x	x-x	x	X
Bruising	x	x-x	x	X
Hoarse Voice	x	x-x	x	X
Abnormal weight gain	x	x (x)	x (x)	X
Cough	x	x (x)	x (x)	X

Table 14: Patient questionnaire reported outcomes for patients prescribed >1000 µg non-extrafine beclomethasone

	Aerochamber®	Volumatic®	95% Confidence Interval	p-value
Total number of patient reported adverse events, n (%)	x (x)	x (x)	x (x)	X
Continual sore mouth	x	x-x	x	X
Oral thrush	x	x-x	x	X
Bruising	x	x-x	x	X
Hoarse Voice	x	x-x	x	X
Abnormal weight gain	x	x (x)	x (x)	X
Cough	x	x (x)	x (x)	X

Table 15: Patient questionnaire reported outcomes for patients prescribed <1000 µg non-extrafine beclomethasone aged <16

	Aerochamber®	Volumatic®	95% Confidence Interval	p-value
Total number of patient reported adverse events, n (%)	x (x)	x (x)	x (x)	X

Continual sore mouth	x	x-x	x	X
Oral thrush	x	x-x	x	X
Bruising	x	x-x	x	X
Hoarse Voice	x	x-x	x	X
Abnormal weight gain	x	x (x)	x (x)	X
Cough	x	x (x)	x (x)	X

Table 16: Patient questionnaire with <1000 µg beclomethasone and aged 16-65

	Aerochamber®	Volumatic®	95% Confidence Interval	p-value
Total number of patient reported adverse events, n (%)	x (x)	x (x)	x (x)	X
Continual sore mouth	x	x-x	x	X
Oral thrush	x	x-x	x	X
Bruising	x	x-x	x	X
Hoarse Voice	x	x-x	x	X
Abnormal weight gain	x	x (x)	x (x)	X
Cough	x	x (x)	x (x)	X

Table 17: Patient questionnaire with >1000 µg beclomethasone and aged <16

	Aerochamber®	Volumatic®	95% Confidence Interval	p-value
Total number of patient reported adverse events, n (%)	x (x)	x (x)	x (x)	X
Continual sore mouth	x	x-x	x	X

Oral thrush	x	x-x	x	X
Bruising	x	x-x	x	X
Hoarse Voice	x	x-x	x	X
Abnormal weight gain	x	x (x)	x (x)	X
Cough	x	x (x)	x (x)	X

Table 18: Patient questionnaire with >1000 µg beclomethasone and aged 16-65

15.2.2 Database adverse events

	Aerochamber®	Volumatic®	95% Confidence Interval	p-value
Total number of database adverse events, n (%)	x (x)	x (x)	x (x)	X
Rash	x	x-x	x	X
Oral thrush	x	x-x	x	X
Adrenal suppression	x	x-x	x	X
Osteoporosis	x	x-x	x	X
Anxiety/depression	x	x (x)	x (x)	X
Cataracts	x	x (x)	x (x)	X
Glaucoma	x	x (x)	x (x)	x

Table 19: Total patient questionnaire reported adverse events

	Aerochamber®	Volumatic®	95% Confidence Interval	p-value
Total number of patient reported adverse events, n (%)	x (x)	x (x)	x (x)	X
Rash	x	x-x	x	X

Oral thrush	x	x-x	x	X
Adrenal suppression	x	x-x	x	X
Osteoporosis	x	x-x	x	X
Anxiety/depression	x	x (x)	x (x)	X
Cataracts	x	x (x)	x (x)	X
Glaucoma	x	x (x)	x (x)	x

Table 20: Patient questionnaire reported outcomes for patients <16

	Aerochamber®	Volumatic®	95% Confidence Interval	p-value
Total number of patient reported adverse events, n (%)	x (x)	x (x)	x (x)	X
Rash	x	x-x	x	X
Oral thrush	x	x-x	x	X
Adrenal suppression	x	x-x	x	X
Osteoporosis	x	x-x	x	X
Anxiety/depression	x	x (x)	x (x)	X
Cataracts	x	x (x)	x (x)	X
Glaucoma	x	x (x)	x (x)	x

Table 21: Patient questionnaire reported outcomes for patients aged 16-65

	Aerochamber®	Volumatic®	95% Confidence Interval	p-value
Total number of patient reported adverse events, n (%)	x (x)	x (x)	x (x)	X

Rash	x	x-x	x	X
Oral thrush	x	x-x	x	X
Adrenal suppression	x	x-x	x	X
Osteoporosis	x	x-x	x	X
Anxiety/depression	x	x (x)	x (x)	X
Cataracts	x	x (x)	x (x)	X
Glaucoma	x	x (x)	x (x)	x

Table 22: Patient questionnaire reported outcomes for patients prescribed <1000 µg non extra fine beclomethasone

	Aerochamber®	Volumatic®	95% Confidence Interval	p-value
Total number of patient reported adverse events, n (%)	x (x)	x (x)	x (x)	X
Rash	x	x-x	x	X
Oral thrush	x	x-x	x	X
Adrenal suppression	x	x-x	x	X
Osteoporosis	x	x-x	x	X
Anxiety/depression	x	x (x)	x (x)	X
Cataracts	x	x (x)	x (x)	X
Glaucoma	x	x (x)	x (x)	x

Table 23: Patient questionnaire reported outcomes for patients prescribed >1000 µg non-extrafine beclomethasone

	Aerochamber®	Volumatic®	95% Confidence Interval	p-value
Total number of patient reported adverse events, n (%)	x (x)	x (x)	x (x)	X

Rash	x	x-x	x	X
Oral thrush	x	x-x	x	X
Adrenal suppression	x	x-x	x	X
Osteoporosis	x	x-x	x	X
Anxiety/depression	x	x (x)	x (x)	X
Cataracts	x	x (x)	x (x)	X
Glaucoma	x	x (x)	x (x)	x

Table 24: Patient questionnaire reported outcomes for patients prescribed <1000 µg non-extrafine beclomethasone aged <16

	Aerochamber®	Volumatic®	95% Confidence Interval	p-value
Total number of patient reported adverse events, n (%)	x (x)	x (x)	x (x)	X
Rash	x	x-x	x	X
Oral thrush	x	x-x	x	X
Adrenal suppression	x	x-x	x	X
Osteoporosis	x	x-x	x	X
Anxiety/depression	x	x (x)	x (x)	X
Cataracts	x	x (x)	x (x)	X
Glaucoma	x	x (x)	x (x)	x

Table 25: Patient questionnaire with <1000 µg beclomethasone and aged 16-65

	Aerochamber®	Volumatic®	95% Confidence Interval	p-value
--	--------------	------------	-------------------------	---------

Total number of patient reported adverse events, n (%)	x (x)	x (x)	x (x)	X
Continual sore mouth	x	x-x	x	X
Oral thrush	x	x-x	x	X
Bruising	x	x-x	x	X
Hoarse Voice	x	x-x	x	X
Abnormal weight gain	x	x (x)	x (x)	X
Cough	x	x (x)	x (x)	X

Table 26: Patient questionnaire with >1000 µg beclomethasone and aged <16

	Aerochamber®	Volumatic®	95% Confidence Interval	p-value
Total number of database adverse events, n (%)	x (x)	x (x)	x (x)	X
Rash	x	x-x	x	X
Oral thrush	x	x-x	x	X
Adrenal suppression	x	x-x	x	X
Osteoporosis	x	x-x	x	X
Anxiety/depression	x	x (x)	x (x)	X
Cataracts	x	x (x)	x (x)	X
Glaucoma	x	x (x)	x (x)	x

Table 27: Patient questionnaire with >1000 µg beclomethasone and aged 16-65

Table 28: Summary statistic of baseline variables overall

		Volumatic®	Aerochamber®	p-value
Total (%)		x (x)	x (x)	x (x)
Age (years)	N (% non-missing)	x (x)	x (x)	x (x)
	Mean (SD)	x (x)	x (x)	x (x)
	Median (IQR)	x (x, x)	x (x, x)	x (x, x)
Gender, n (%)	Male	x (x)	x (x)	x (x)
	Female	x (x)	x (x)	x (x)
BMI (kg/m ²)	N (% non-missing)	x (x)	x (x)	x (x)
	Mean (SD)	x (x)	x (x)	x (x)
	Median (IQR)	x (x, x)	x (x, x)	x (x, x)
BMI (categorised), n (%)	Underweight	x (x)	x (x)	x (x)
	Normal	x (x)	x (x)	x (x)
	Overweight	x (x)	x (x)	x (x)
	Obese	x (x)	x (x)	x (x)
Smoking status, n (%)	Current smoker	x (x)	x (x)	x (x)
	Ex-smoker	x (x)	x (x)	x (x)
	Mean (SD)	x (x)	x (x)	x (x)
	Median (IQR)	x (x, x)	x (x, x)	x (x, x)
Average SABA daily dose	N (% non-missing)	x (x)	x (x)	x (x)
	Mean (SD)	x (x)	x (x)	x (x)
	Median (IQR)	x (x, x)	x (x, x)	x (x, x)
Average SABA daily dose (categorised), n (%)	Low	x (x)	x (x)	x (x)
	Medium	x (x)	x (x)	x (x)
	High	x (x)	x (x)	x (x)
	Medium	x (x)	x (x)	x (x)
	High	x (x)	x (x)	x (x)
	Median (IQR)	x (x, x)	x (x, x)	x (x, x)
FEV ₁ /FVC ratio	N (% non-missing)	x (x)	x (x)	x (x)
	Mean (SD)	x (x)	x (x)	x (x)
	Median (IQR)	x (x, x)	x (x, x)	x (x, x)
Exacerbation count	N (% non-missing)	x (x)	x (x)	x (x)
	Mean (SD)	x (x)	x (x)	x (x)
	Median (IQR)	x (x, x)	x (x, x)	x (x, x)

Oral corticosteroid prescriptions	N (% non-missing)	x (x)	x (x)	x (x)
	Mean (SD)	x (x)	x (x)	x (x)
	Median (IQR)	x (x, x)	x (x, x)	x (x, x)
Antibiotic prescriptions for LRTI	N (% non-missing)	x (x)	x (x)	x (x)
	Mean (SD)	x (x)	x (x)	x (x)
	Median (IQR)	x (x, x)	x (x, x)	x (x, x)
% Predicted Peak Flow	N (% non-missing)	x (x)	x (x)	x (x)
	Mean (SD)	x (x)	x (x)	x (x)
	Median (IQR)	x (x, x)	x (x, x)	x (x, x)

Table 29: Summary statistics for diagnoses of co-morbidities at baseline

		Volumatic®	Aerochamber®	p-value
Total (%)		x (x)	x (x)	x (x)
Pneumonia	N (% non-missing)	x (x)	x (x)	x (x)
	Mean (SD)	x (x)	x (x)	x (x)
	Median (IQR)	x (x, x)	x (x, x)	x (x, x)
Diabetes	N (% non-missing)	x (x)	x (x)	x (x)
	Mean (SD)	x (x)	x (x)	x (x)
	Median (IQR)	x (x, x)	x (x, x)	x (x, x)
Ischaemic heart disease	N (% non-missing)	x (x)	x (x)	x (x)
	Mean (SD)	x (x)	x (x)	x (x)
	Median (IQR)	x (x, x)	x (x, x)	x (x, x)
Rhinitis	N (% non-missing)	x (x)	x (x)	x (x)
	Mean (SD)	x (x)	x (x)	x (x)
	Median (IQR)	x (x, x)	x (x, x)	x (x, x)
Eczema	N (% non-missing)	x (x)	x (x)	x (x)
	Mean (SD)	x (x)	x (x)	x (x)
	Median (IQR)	x (x, x)	x (x, x)	x (x, x)
Osteoporosis	N (% non-missing)	x (x)	x (x)	x (x)
	Mean (SD)	x (x)	x (x)	x (x)
	Median (IQR)	x (x, x)	x (x, x)	x (x, x)
Charlson comorbidity index, n (%)	0	x (x)	x (x)	x (x)
	1-4	x (x)	x (x)	x (x)
	5+	x (x)	x (x)	x (x)

		Volumatic®	Aerochamber®	p-value
Total (%)		x (x)	x (x)	x (x)
Age (years)	N (% non-missing)	x (x)	x (x)	x (x)
	Mean (SD)	x (x)	x (x)	x (x)
	Median (IQR)	x (x, x)	x (x, x)	x (x, x)
Gender, n (%)	Male	x (x)	x (x)	x (x)
	Female	x (x)	x (x)	x (x)
BMI (kg/m ²)	N (% non-missing)	x (x)	x (x)	x (x)
	Mean (SD)	x (x)	x (x)	x (x)
	Median (IQR)	x (x, x)	x (x, x)	x (x, x)
BMI (categorised), n (%)	Underweight	x (x)	x (x)	x (x)
	Normal	x (x)	x (x)	x (x)
	Overweight	x (x)	x (x)	x (x)
	Obese	x (x)	x (x)	x (x)
Smoking status, n (%)	Current smoker	x (x)	x (x)	x (x)
	Ex-smoker	x (x)	x (x)	x (x)
	Mean (SD)	x (x)	x (x)	x (x)
	Median (IQR)	x (x, x)	x (x, x)	x (x, x)
Average SABA daily dose	N (% non-missing)	x (x)	x (x)	x (x)
	Mean (SD)	x (x)	x (x)	x (x)
	Median (IQR)	x (x, x)	x (x, x)	x (x, x)
Average SABA daily dose (categorised), n (%)	Low	x (x)	x (x)	x (x)
	Medium	x (x)	x (x)	x (x)
	High	x (x)	x (x)	x (x)
	Medium	x (x)	x (x)	x (x)
	High	x (x)	x (x)	x (x)
	Median (IQR)	x (x, x)	x (x, x)	x (x, x)
FEV ₁ /FVC ratio	N (% non-missing)	x (x)	x (x)	x (x)
	Mean (SD)	x (x)	x (x)	x (x)
	Median (IQR)	x (x, x)	x (x, x)	x (x, x)
Exacerbation count	N (% non-missing)	x (x)	x (x)	x (x)
	Mean (SD)	x (x)	x (x)	x (x)

	Median (IQR)	x (x, x)	x (x, x)	x (x, x)
Oral corticosteroids prescriptions	N (% non-missing)	x (x)	x (x)	x (x)
	Mean (SD)	x (x)	x (x)	x (x)
	Median (IQR)	x (x, x)	x (x, x)	x (x, x)
Antibiotic prescriptions for LRTI	N (% non-missing)	x (x)	x (x)	x (x)
	Mean (SD)	x (x)	x (x)	x (x)
	Median (IQR)	x (x, x)	x (x, x)	x (x, x)
% Predicted Peak Flow	N (% non-missing)	x (x)	x (x)	x (x)
	Mean (SD)	x (x)	x (x)	x (x)
	Median (IQR)	x (x, x)	x (x, x)	x (x, x)

Table 30: Summary statistics for <16 age group

		Volumatic®	Aerochamber®	p-value
Total (%)		x (x)	x (x)	x (x)
Pneumonia	N (% non-missing)	x (x)	x (x)	x (x)
	Mean (SD)	x (x)	x (x)	x (x)
	Median (IQR)	x (x, x)	x (x, x)	x (x, x)
Diabetes	N (% non-missing)	x (x)	x (x)	x (x)
	Mean (SD)	x (x)	x (x)	x (x)
	Median (IQR)	x (x, x)	x (x, x)	x (x, x)
Ischaemic heart disease	N (% non-missing)	x (x)	x (x)	x (x)
	Mean (SD)	x (x)	x (x)	x (x)
	Median (IQR)	x (x, x)	x (x, x)	x (x, x)
Rhinitis	N (% non-missing)	x (x)	x (x)	x (x)
	Mean (SD)	x (x)	x (x)	x (x)
	Median (IQR)	x (x, x)	x (x, x)	x (x, x)
Eczema	N (% non-missing)	x (x)	x (x)	x (x)
	Mean (SD)	x (x)	x (x)	x (x)
	Median (IQR)	x (x, x)	x (x, x)	x (x, x)
Osteoporosis	N (% non-missing)	x (x)	x (x)	x (x)
	Mean (SD)	x (x)	x (x)	x (x)
	Median (IQR)	x (x, x)	x (x, x)	x (x, x)
Charlson comorbidity index, n (%)	0	x (x)	x (x)	x (x)
	1-4	x (x)	x (x)	x (x)
	5+	x (x)	x (x)	x (x)

Table 31: Summary statistics for comorbidities in <16 age group

		Volumatic®	Aerochamber®	p-value
Total (%)		x (x)	x (x)	x (x)
Age (years)	N (% non-missing)	x (x)	x (x)	x (x)
	Mean (SD)	x (x)	x (x)	x (x)
	Median (IQR)	x (x, x)	x (x, x)	x (x, x)
Gender, n (%)	Male	x (x)	x (x)	x (x)
	Female	x (x)	x (x)	x (x)
BMI (kg/m ²)	N (% non-missing)	x (x)	x (x)	x (x)
	Mean (SD)	x (x)	x (x)	x (x)
	Median (IQR)	x (x, x)	x (x, x)	x (x, x)
BMI (categorised), n (%)	Underweight	x (x)	x (x)	x (x)
	Normal	x (x)	x (x)	x (x)
	Overweight	x (x)	x (x)	x (x)
	Obese	x (x)	x (x)	x (x)
Smoking status, n (%)	Current smoker	x (x)	x (x)	x (x)
	Ex-smoker	x (x)	x (x)	x (x)
	Mean (SD)	x (x)	x (x)	x (x)
	Median (IQR)	x (x, x)	x (x, x)	x (x, x)
Average SABA daily dose	N (% non-missing)	x (x)	x (x)	x (x)
	Mean (SD)	x (x)	x (x)	x (x)
	Median (IQR)	x (x, x)	x (x, x)	x (x, x)
Average SABA daily dose (categorised), n (%)	Low	x (x)	x (x)	x (x)
	Medium	x (x)	x (x)	x (x)
	High	x (x)	x (x)	x (x)
	Medium	x (x)	x (x)	x (x)
	High	x (x)	x (x)	x (x)
	Median (IQR)	x (x, x)	x (x, x)	x (x, x)
FEV ₁ /FVC ratio	N (% non-missing)	x (x)	x (x)	x (x)
	Mean (SD)	x (x)	x (x)	x (x)
	Median (IQR)	x (x, x)	x (x, x)	x (x, x)
Exacerbation count	N (% non-missing)	x (x)	x (x)	x (x)
	Mean (SD)	x (x)	x (x)	x (x)
	Median (IQR)	x (x, x)	x (x, x)	x (x, x)

Oral corticosteroid prescriptions	N (% non-missing)	x (x)	x (x)	x (x)
	Mean (SD)	x (x)	x (x)	x (x)
	Median (IQR)	x (x, x)	x (x, x)	x (x, x)
Antibiotic prescriptions for LRTI	N (% non-missing)	x (x)	x (x)	x (x)
	Mean (SD)	x (x)	x (x)	x (x)
	Median (IQR)	x (x, x)	x (x, x)	x (x, x)
% Predicted Peak Flow	N (% non-missing)	x (x)	x (x)	x (x)
	Mean (SD)	x (x)	x (x)	x (x)
	Median (IQR)	x (x, x)	x (x, x)	x (x, x)

Table 32: Summary statistics for mean <1000µg beclomethasone per day

		Volumatic®	Aerochamber®	p-value
	Total (%)	x (x)	x (x)	x (x)
Pneumonia	N (% non-missing)	x (x)	x (x)	x (x)
	Mean (SD)	x (x)	x (x)	x (x)
	Median (IQR)	x (x, x)	x (x, x)	x (x, x)
Diabetes	N (% non-missing)	x (x)	x (x)	x (x)
	Mean (SD)	x (x)	x (x)	x (x)
	Median (IQR)	x (x, x)	x (x, x)	x (x, x)
Ischaemic heart disease	N (% non-missing)	x (x)	x (x)	x (x)
	Mean (SD)	x (x)	x (x)	x (x)
	Median (IQR)	x (x, x)	x (x, x)	x (x, x)
Rhinitis	N (% non-missing)	x (x)	x (x)	x (x)
	Mean (SD)	x (x)	x (x)	x (x)
	Median (IQR)	x (x, x)	x (x, x)	x (x, x)
Eczema	N (% non-missing)	x (x)	x (x)	x (x)
	Mean (SD)	x (x)	x (x)	x (x)
	Median (IQR)	x (x, x)	x (x, x)	x (x, x)
Osteoporosis	N (% non-missing)	x (x)	x (x)	x (x)
	Mean (SD)	x (x)	x (x)	x (x)
	Median (IQR)	x (x, x)	x (x, x)	x (x, x)
Charlson comorbidity index, n (%)	0	x (x)	x (x)	x (x)
	1-4	x (x)	x (x)	x (x)
	5+	x (x)	x (x)	x (x)

Table 33: Summary statistics for mean ICS <1000µg dose per day

		Volumatic®	Aerochamber®	p-value
Total (%)		x (x)	x (x)	x (x)
Age (years)	N (% non-missing)	x (x)	x (x)	x (x)
	Mean (SD)	x (x)	x (x)	x (x)
	Median (IQR)	x (x, x)	x (x, x)	x (x, x)
Gender, n (%)	Male	x (x)	x (x)	x (x)
	Female	x (x)	x (x)	x (x)
BMI (kg/m ²)	N (% non-missing)	x (x)	x (x)	x (x)
	Mean (SD)	x (x)	x (x)	x (x)
	Median (IQR)	x (x, x)	x (x, x)	x (x, x)
BMI (categorised), n (%)	Underweight	x (x)	x (x)	x (x)
	Normal	x (x)	x (x)	x (x)
	Overweight	x (x)	x (x)	x (x)
	Obese	x (x)	x (x)	x (x)
Smoking status, n (%)	Current smoker	x (x)	x (x)	x (x)
	Ex-smoker	x (x)	x (x)	x (x)
	Mean (SD)	x (x)	x (x)	x (x)
	Median (IQR)	x (x, x)	x (x, x)	x (x, x)
Average SABA daily dose	N (% non-missing)	x (x)	x (x)	x (x)
	Mean (SD)	x (x)	x (x)	x (x)
	Median (IQR)	x (x, x)	x (x, x)	x (x, x)
Average SABA daily dose (categorised), n (%)	Low	x (x)	x (x)	x (x)
	Medium	x (x)	x (x)	x (x)
	High	x (x)	x (x)	x (x)
	Medium	x (x)	x (x)	x (x)
	High	x (x)	x (x)	x (x)
	Median (IQR)	x (x, x)	x (x, x)	x (x, x)
FEV ₁ /FVC ratio	N (% non-missing)	x (x)	x (x)	x (x)
	Mean (SD)	x (x)	x (x)	x (x)
	Median (IQR)	x (x, x)	x (x, x)	x (x, x)
Exacerbation count	N (% non-missing)	x (x)	x (x)	x (x)
	Mean (SD)	x (x)	x (x)	x (x)
	Median (IQR)	x (x, x)	x (x, x)	x (x, x)
Oral corticosteroid	N (% non-missing)	x (x)	x (x)	x (x)

s prescriptions	Mean (SD)	x (x)	x (x)	x (x)
	Median (IQR)	x (x, x)	x (x, x)	x (x, x)
Antibiotic prescriptions for LRTI	N (% non-missing)	x (x)	x (x)	x (x)
	Mean (SD)	x (x)	x (x)	x (x)
	Median (IQR)	x (x, x)	x (x, x)	x (x, x)
% Predicted Peak Flow	N (% non-missing)	x (x)	x (x)	x (x)
	Mean (SD)	x (x)	x (x)	x (x)
	Median (IQR)	x (x, x)	x (x, x)	x (x, x)

Table 34: Summary statistics for 16-65 year olds

		Volumatic®	Aerochamber®	p-value
Total (%)		x (x)	x (x)	x (x)
Pneumonia	N (% non-missing)	x (x)	x (x)	x (x)
	Mean (SD)	x (x)	x (x)	x (x)
	Median (IQR)	x (x, x)	x (x, x)	x (x, x)
Diabetes	N (% non-missing)	x (x)	x (x)	x (x)
	Mean (SD)	x (x)	x (x)	x (x)
	Median (IQR)	x (x, x)	x (x, x)	x (x, x)
Ischaemic heart disease	N (% non-missing)	x (x)	x (x)	x (x)
	Mean (SD)	x (x)	x (x)	x (x)
	Median (IQR)	x (x, x)	x (x, x)	x (x, x)
Rhinitis	N (% non-missing)	x (x)	x (x)	x (x)
	Mean (SD)	x (x)	x (x)	x (x)
	Median (IQR)	x (x, x)	x (x, x)	x (x, x)
Eczema	N (% non-missing)	x (x)	x (x)	x (x)
	Mean (SD)	x (x)	x (x)	x (x)
	Median (IQR)	x (x, x)	x (x, x)	x (x, x)
Osteoporosis	N (% non-missing)	x (x)	x (x)	x (x)
	Mean (SD)	x (x)	x (x)	x (x)
	Median (IQR)	x (x, x)	x (x, x)	x (x, x)
Charlson comorbidity index, n (%)	0	x (x)	x (x)	x (x)
	1-4	x (x)	x (x)	x (x)
	5+	x (x)	x (x)	x (x)

Table 35: Summary co-morbidities for 16-65 year olds

	Volumatic®	Aerochamber®	p-value
--	------------	--------------	---------

	Total (%)	x (x)	x (x)	x (x)
Age (years)	N (% non-missing)	x (x)	x (x)	x (x)
	Mean (SD)	x (x)	x (x)	x (x)
	Median (IQR)	x (x, x)	x (x, x)	x (x, x)
Gender, n (%)	Male	x (x)	x (x)	x (x)
	Female	x (x)	x (x)	x (x)
BMI (kg/m ²)	N (% non-missing)	x (x)	x (x)	x (x)
	Mean (SD)	x (x)	x (x)	x (x)
	Median (IQR)	x (x, x)	x (x, x)	x (x, x)
BMI (categorised), n (%)	Underweight	x (x)	x (x)	x (x)
	Normal	x (x)	x (x)	x (x)
	Overweight	x (x)	x (x)	x (x)
	Obese	x (x)	x (x)	x (x)
Smoking status, n (%)	Current smoker	x (x)	x (x)	x (x)
	Ex-smoker	x (x)	x (x)	x (x)
	Mean (SD)	x (x)	x (x)	x (x)
	Median (IQR)	x (x, x)	x (x, x)	x (x, x)
Average SABA daily dose	N (% non-missing)	x (x)	x (x)	x (x)
	Mean (SD)	x (x)	x (x)	x (x)
	Median (IQR)	x (x, x)	x (x, x)	x (x, x)
Average SABA daily dose (categorised), n (%)	Low	x (x)	x (x)	x (x)
	Medium	x (x)	x (x)	x (x)
	High	x (x)	x (x)	x (x)
	Medium	x (x)	x (x)	x (x)
	High	x (x)	x (x)	x (x)
	Median (IQR)	x (x, x)	x (x, x)	x (x, x)
FEV ₁ /FVC ratio	N (% non-missing)	x (x)	x (x)	x (x)
	Mean (SD)	x (x)	x (x)	x (x)
	Median (IQR)	x (x, x)	x (x, x)	x (x, x)
Exacerbation count	N (% non-missing)	x (x)	x (x)	x (x)
	Mean (SD)	x (x)	x (x)	x (x)
	Median (IQR)	x (x, x)	x (x, x)	x (x, x)
Oral corticosteroid	N (% non-missing)	x (x)	x (x)	x (x)
	Mean (SD)	x (x)	x (x)	x (x)

s prescriptions	Median (IQR)	x (x, x)	x (x, x)	x (x, x)
Antibiotic prescriptions for LRTI	N (% non-missing)	x (x)	x (x)	x (x)
	Mean (SD)	x (x)	x (x)	x (x)
	Median (IQR)	x (x, x)	x (x, x)	x (x, x)
% Predicted Peak Flow	N (% non-missing)	x (x)	x (x)	x (x)
	Mean (SD)	x (x)	x (x)	x (x)
	Median (IQR)	x (x, x)	x (x, x)	x (x, x)

Table 36: Summary statistics for mean dose of 1000+ µg beclomethasone

		Volumatic®	Aerochamber®	p-value
Total (%)		x (x)	x (x)	x (x)
Pneumonia	N (% non-missing)	x (x)	x (x)	x (x)
	Mean (SD)	x (x)	x (x)	x (x)
	Median (IQR)	x (x, x)	x (x, x)	x (x, x)
Diabetes	N (% non-missing)	x (x)	x (x)	x (x)
	Mean (SD)	x (x)	x (x)	x (x)
	Median (IQR)	x (x, x)	x (x, x)	x (x, x)
Ischaemic heart disease	N (% non-missing)	x (x)	x (x)	x (x)
	Mean (SD)	x (x)	x (x)	x (x)
	Median (IQR)	x (x, x)	x (x, x)	x (x, x)
Rhinitis	N (% non-missing)	x (x)	x (x)	x (x)
	Mean (SD)	x (x)	x (x)	x (x)
	Median (IQR)	x (x, x)	x (x, x)	x (x, x)
Eczema	N (% non-missing)	x (x)	x (x)	x (x)
	Mean (SD)	x (x)	x (x)	x (x)
	Median (IQR)	x (x, x)	x (x, x)	x (x, x)
Osteoporosis	N (% non-missing)	x (x)	x (x)	x (x)
	Mean (SD)	x (x)	x (x)	x (x)
	Median (IQR)	x (x, x)	x (x, x)	x (x, x)
Charlson comorbidity index, n (%)	0	x (x)	x (x)	x (x)
	1-4	x (x)	x (x)	x (x)
	5+	x (x)	x (x)	x (x)

Table 37: Summary statistics for mean dose (1000+µg of beclomethasone)

		Volumatic®	Aerochamber®	p-value
Total (%)		x (x)	x (x)	x (x)

Age (years)	N (% non-missing)	x (x)	x (x)	x (x)
	Mean (SD)	x (x)	x (x)	x (x)
	Median (IQR)	x (x, x)	x (x, x)	x (x, x)
Gender, n (%)	Male	x (x)	x (x)	x (x)
	Female	x (x)	x (x)	x (x)
BMI (kg/m ²)	N (% non-missing)	x (x)	x (x)	x (x)
	Mean (SD)	x (x)	x (x)	x (x)
	Median (IQR)	x (x, x)	x (x, x)	x (x, x)
BMI (categorised), n (%)	Underweight	x (x)	x (x)	x (x)
	Normal	x (x)	x (x)	x (x)
	Overweight	x (x)	x (x)	x (x)
	Obese	x (x)	x (x)	x (x)
Smoking status, n (%)	Current smoker	x (x)	x (x)	x (x)
	Ex-smoker	x (x)	x (x)	x (x)
	Mean (SD)	x (x)	x (x)	x (x)
	Median (IQR)	x (x, x)	x (x, x)	x (x, x)
Average SABA daily dose	N (% non-missing)	x (x)	x (x)	x (x)
	Mean (SD)	x (x)	x (x)	x (x)
	Median (IQR)	x (x, x)	x (x, x)	x (x, x)
Average SABA daily dose (categorised), n (%)	Low	x (x)	x (x)	x (x)
	Medium	x (x)	x (x)	x (x)
	High	x (x)	x (x)	x (x)
	Medium	x (x)	x (x)	x (x)
	High	x (x)	x (x)	x (x)
	Median (IQR)	x (x, x)	x (x, x)	x (x, x)
FEV ₁ /FVC ratio	N (% non-missing)	x (x)	x (x)	x (x)
	Mean (SD)	x (x)	x (x)	x (x)
	Median (IQR)	x (x, x)	x (x, x)	x (x, x)
Exacerbation count	N (% non-missing)	x (x)	x (x)	x (x)
	Mean (SD)	x (x)	x (x)	x (x)
	Median (IQR)	x (x, x)	x (x, x)	x (x, x)
Oral corticosteroids prescriptions	N (% non-missing)	x (x)	x (x)	x (x)
	Mean (SD)	x (x)	x (x)	x (x)
	Median (IQR)	x (x, x)	x (x, x)	x (x, x)

Antibiotic prescriptions for LRTI	N (% non-missing)	x (x)	x (x)	x (x)
	Mean (SD)	x (x)	x (x)	x (x)
	Median (IQR)	x (x, x)	x (x, x)	x (x, x)
% Predicted Peak Flow	N (% non-missing)	x (x)	x (x)	x (x)
	Mean (SD)	x (x)	x (x)	x (x)
	Median (IQR)	x (x, x)	x (x, x)	x (x, x)

Table 38: Summary statistics for <16 and high dose ICS

		Volumatic®	Aerochamber®	p-value
Total (%)		x (x)	x (x)	x (x)
Pneumonia	N (% non-missing)	x (x)	x (x)	x (x)
	Mean (SD)	x (x)	x (x)	x (x)
	Median (IQR)	x (x, x)	x (x, x)	x (x, x)
Diabetes	N (% non-missing)	x (x)	x (x)	x (x)
	Mean (SD)	x (x)	x (x)	x (x)
	Median (IQR)	x (x, x)	x (x, x)	x (x, x)
Ischaemic heart disease	N (% non-missing)	x (x)	x (x)	x (x)
	Mean (SD)	x (x)	x (x)	x (x)
	Median (IQR)	x (x, x)	x (x, x)	x (x, x)
Rhinitis	N (% non-missing)	x (x)	x (x)	x (x)
	Mean (SD)	x (x)	x (x)	x (x)
	Median (IQR)	x (x, x)	x (x, x)	x (x, x)
Eczema	N (% non-missing)	x (x)	x (x)	x (x)
	Mean (SD)	x (x)	x (x)	x (x)
	Median (IQR)	x (x, x)	x (x, x)	x (x, x)
Osteoporosis	N (% non-missing)	x (x)	x (x)	x (x)
	Mean (SD)	x (x)	x (x)	x (x)
	Median (IQR)	x (x, x)	x (x, x)	x (x, x)
Charlson comorbidity index, n (%)	0	x (x)	x (x)	x (x)
	1-4	x (x)	x (x)	x (x)
	5+	x (x)	x (x)	x (x)

Table 39: Summary statistics for <16 and high dose ICS

		Volumatic®	Aerochamber®	p-value
Total (%)		x (x)	x (x)	x (x)
Age (years)	N (% non-missing)	x (x)	x (x)	x (x)

	Mean (SD)	x (x)	x (x)	x (x)
	Median (IQR)	x (x, x)	x (x, x)	x (x, x)
Gender, n (%)	Male	x (x)	x (x)	x (x)
	Female	x (x)	x (x)	x (x)
BMI (kg/m ²)	N (% non-missing)	x (x)	x (x)	x (x)
